1.15 SAMPLE SIZE AND POWER CONSIDERATION

Aim 1: The sample size considerations for this study are based on the number of available sites given the project scope and timeline: N=18 sites will participate. With N=9 randomized to each condition, correlation of 0.7 between pairs of 11 repeated measures, the detectable adjusted effect size for the site-level outcomes is approximately 1.2, expressed as Cohen's d, difference between trial arm means in the standard deviation units. If the observed differences are smaller than 1.2 of the standard deviation, statistical significance will not be reached, then the estimate of the effect size will be obtained and used to formally power a subsequent R01-size study that will be proposed based on the results obtained in this R15 project. For the beneficiary-level outcomes, we assumed an average N=750 beneficiaries analyzed per site and conservative intraclass correlation coefficient of 0.01 for planning purposes to obtain the design effect factor DEFF=8.49. In the comparison of the trial arms for the beneficiary-level outcomes, the sample size adjusted for the design is 795 per trial arm, and it allows to detect the effect size as small as 0.14. Larger effects were seen in the preliminary studies for the beneficiary-level data, and 1/3 of the standard deviation or larger is often used as a threshold for clinical significance.⁸⁸⁻⁸⁹ Since even small effects could be detected as statistically significant, the study is well powered to detect any meaningful differences between IF and IF+EF in beneficiary outcomes. The tests of mediation effects in Aim 2 will have an even greater power because of further reduction in error variance due to controlling for the mediator. Aim 3 benchmarks the outcomes against the pre-intervention period and has no associated hypotheses. Thus, power considerations are not applicable. Similarly, exploratory aims 4-6 have no associated hypotheses; thus, the results will be used for generation of hypotheses for the future R01-scope trial.

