1. GVSU
2. MDHHS

We will update the IRBs as changes occur over the course of the study.

Data Use Agreements (DUA)

In compliance with GVSU policy, we will collaborate with the Center for Scholarly and Creative Excellence to fully execute the following DUAs prior to data collection or use.

1. Between the university and MDHHS for: MDS (2017-2021), administrative (2018), Continuous Quality Assessment Review (CQAR) scores (2015-2017), and cost (2020) data
2. Between the university and the 18 sites and CIM for data from EHRs MDS, person centered service plan (PSCP), and progress notes (PNs) data (2017-21).

We will update the DUAs as changes occur over the course of the study.

Contracts to be Execute

In compliance with GVSU policy, we will collaborate with the Center for Scholarly and Creative Excellence to fully execute the following contracts prior to working with a site or data analysis by the statistician.

1. Between the university and the 18 site prior to initiating the project (role and responsibilities; training; tasks; duties; timelines; actions; and use of CAPABLE with fidelity to the intervention).
2. Between the university and the biostatistician prior to data analysis.

We will update the contracts as changes occur over the course of the study.

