1.16 RANDOMIZATION

Randomization for this study occurs at the site level. Sites will be randomized by the PM, to **Arm 1** (MiCAP with IF) or **Arm 2** (MiCAP with IF+EF) using the following steps.

Step 1: Data on site size (number of beneficiaries [patients]) and Clinical Quality Assessment Review (CQAR) scores will be obtained.

Step 2: We will block sites in pairs with similar size and CQAR scores, and flip a coin to determine **Arm 1** or **Arm 2** assignment for study.

The PM will maintain a confidential file documenting study Arm by site. Only the PI/PM will know Arm assignment by site.

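### The beneficiary-level detectable effect of 0.14 uses normal quantiles; with the degrees of freedom that 18 randomised sites allow it is 0.15, and power at 0.14 is about 75%.

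*Combined protocol and SAP*

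**What the plan says.** Section 1.16 makes the site the unit of allocation ("Randomization for this study occurs at the site level"), and Section 1.15 has 18 sites ("With N=9 randomized to each condition").

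For beneficiary outcomes, Section 1.15 explains that "we assumed an average N=750 beneficiaries analyzed per site and conservative intraclass correlation coefficient of 0.01 for planning purposes". These inputs yield its inflation factor of 8.49. It then reports that "the sample size adjusted for the design is 795 per trial arm, and it allows to detect the effect size as small as 0.14". From this it concludes that small effects are detectable and that power is ample for any difference that matters, citing one third of a standard deviation as a common threshold for clinical significance. It gives no alpha, sidedness, power, degrees of freedom, source for the ICC or range of ICCs.

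The same section puts the detectable site-level effect at approximately 1.2, with a correlation of 0.7 among 11 repeated measures.

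Section 1.14 (Aim A1) plans a generalized linear model for beneficiary outcomes with a random effect of site and the baseline value of each outcome as a covariate. It names no degrees-of-freedom method for the arm coefficient.

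**The concern.** Dividing the beneficiary count by the design effect gives the right variance for the arm difference under the stated ICC. It does not give the right reference distribution. The between-site variance has to be estimated from 18 sites, so the arm test has at most 18 − 2 = 16 degrees of freedom, however many beneficiaries each site contributes. Normal quantiles treat the comparison as if 1,590 people had been randomised independently.

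Two things are at stake. The planning figure is somewhat too favourable, and it supports a statement about small effects. In addition, Section 1.14 leaves the reference distribution for the arm coefficient open. If the analysis used large-sample values, the test would exceed its nominal 5% level.

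**Working it through.** **Inputs.** From Section 1.15: 9 sites per arm, mean 750 beneficiaries per site, ICC 0.01, correlation 0.7 among 11 repeated measures. Inferred: two-sided 5% and 80% power, the usual pair that returns 0.14. (Two-sided 5% with 90% power gives 0.163; one-sided 5% with 80% power gives 0.125.)

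**Reproducing the plan's figure.**
- Design effect: 1 + (750 − 1) × 0.01 = 8.49.
- Effective sample per arm: 9 × 750 / 8.49 = 6750 / 8.49 = 795.
- Standard error in SD units: √(2/795) = 0.0502.
- Normal quantiles: (1.960 + 0.842) × 0.0502 = 2.802 × 0.0502 = 0.1405, the stated 0.14.

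**Same standard error, site-based degrees of freedom.** For 80% power with a noncentral t on 16 degrees of freedom, the required ratio of effect to standard error is 2.985 rather than 2.802.
- Detectable effect: 2.985 × 0.0502 = 0.150.
- Power at 0.14: 74.6%.
- With 14 degrees of freedom (site size and quality score also fitted): 0.151, and power 73.8%.

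More beneficiaries would recover little. At ICC 0.01, as site size grows without limit, the detectable effect tends to 2.985 × √(2 × 0.01 / 9) = 0.141.

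**The site-level figure in the same section.**
- Variance factor for the mean of 11 measures: (1 + 10 × 0.7) / 11 = 0.727.
- Standard error: √(2 × 0.727 / 9) = 0.402.
- Normal quantiles: 2.802 × 0.402 = 1.13.
- t on 16 degrees of freedom: 2.985 × 0.402 = 1.20, in line with the stated value.

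**Sensitivity to the ICC.** Equal site sizes, 16 degrees of freedom, 80% power. ICCs other than 0.01 are assumptions.

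| ICC | Design effect | Detectable effect | Power at 1/3 SD |
|---|---|---|---|
| 0.01 | 8.49 | 0.15 | >99.9% |
| 0.02 | 15.98 | 0.21 | 99.5% |
| 0.03 | 23.47 | 0.25 | 96% |
| 0.05 | 38.45 | 0.32 | 83% |

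The detectable effect reaches 1/3 SD at an ICC of about 0.055.

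**Test level if large-sample values were used.** P(|t| > 1.96) on 16 degrees of freedom is 6.8%.

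**The case against.** The strongest reply is that nothing has been miscalculated and little changes. The design effect, the 795 and the 0.14 all follow from the formula used. The shift is 0.01 SD on secondary outcomes, and the number of sites is fixed by availability. Baseline adjustment, planned in Section 1.14 but not credited in Section 1.15, could offset it: with an assumed baseline-to-outcome correlation of 0.35 at both levels, 0.150 × √(1 − 0.35²) = 0.14. All of this stands, and it limits the point to a modest correction. It does not rescue the figure as stated, because the section makes no appeal to baseline adjustment.

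A reader might also infer more than the documents support:

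- *That the claim of adequate power collapses.* It does not. Against the plan's own threshold of 1/3 SD, it fails only at an ICC about five and a half times the planning value.
- *That unequal site sizes greatly worsen the figure.* Sites do differ in size ("We will block sites in pairs with similar size and CQAR scores"), and a design effect that weights sites by size would suggest a large loss. The planned random-site model does not weight that way. With about 750 beneficiaries per site, its weights, 1/(ICC + (1 − ICC)/m) for a site of size m, are nearly equal. At ICC 0.01 and assumed size CVs up to 0.8, unequal sizes add at most about 0.006.
- *That scoring by site staff raises the ICC.* Section 1.12 describes the MDS-HC as self-reported, and the documents give no evidence on clustering.
- *That 1.2 proves use of t on 16 degrees of freedom.* It is stated only as approximate. Fourteen degrees of freedom give 1.21, and normal quantiles at 85% power give 1.20. It is consistent with t on 16 and not with normal quantiles at 80% power, so the two figures appear to treat the same sites differently.
- *That the trial will run at 6.8%.* Section 1.14 names no method, so that rate is conditional.

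**Conclusion.** The point holds in a limited form. With two-sided 5% and 80% power, the detectable beneficiary-level effect is 0.15 rather than 0.14, and power at 0.14 is about 75% rather than 80%. The cause is the omitted site-based degrees of freedom; the variance calculation is sound under its inputs. The result rests on the plan's own 9 sites per arm, 750 per site and ICC 0.01, on the inferred alpha and power, and on no credit for baseline adjustment.

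The conclusion about differences of 1/3 SD survives. The statement about small effects depends chiefly on the ICC: doubling it to 0.02 moves the detectable effect to 0.21. The documents offer no support for regarding 0.01 as a cautious choice.

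**What to change.** 1. In Section 1.15, restate 0.14 as 0.15, giving two-sided alpha, power and degrees of freedom.
2. In Section 1.14, specify that the arm coefficient in the beneficiary models is tested with site-based degrees of freedom (Kenward-Roger or between-within, at most 16).
3. Replace the description of the ICC as conservative with a short table of detectable effects over ICC 0.01 to 0.05. Ideally, estimate the ICC of each outcome from pre-intervention MDS records; the data use agreement in Section 1.8 already covers MDS data from 2017.
4. If credit is wanted for baseline adjustment, state the assumed correlation.

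The cost is a few sentences and, for the ICC estimates, one descriptive run on data already agreed. No design change is needed. The stated figure becomes slightly less favourable, though baseline adjustment may recover some precision.

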1.3 SPECIFIC AIMS

The **specific aims** are as follows.

Aim A1 To test the effects of MiCAP with IF alone versus MiCAP with IF+EF with respect to the site-level outcomes of adoption and sustainability (**primary**) and beneficiary-level outcomes of ADL/IADLs, pain, depression, falls, emergency department (ED) visits and hospitalizations (**secondary**) over the next 12 months.

Aim A2 Mechanism-of-action To determine whether the effects of EF+IF versus IF on primary outcomes are mediated by clinician attitude or self-efficacy at 9 months.

Aim A3 To benchmark the effects of IF and EF+IF on beneficiary outcomes following implementation as compared to pre-intervention.

Exploratory Aim A4 To compare the primary and secondary outcomes within 12 months, potential mediators at 9 months, and baseline leadership and readiness for sites with SIC of >50% versus sites with SIC \leq 50% at 6 months in each arm.

Exploratory Aim A5 To explore whether baseline site leadership and readiness moderate the impact of EF+IF compared to IF on primary and secondary outcomes within 12 months in order to determine which sites may require facilitation that is more intensive.

Exploratory Aim A6 To evaluate clinician satisfaction at 1 month, and the cost of implementation and policy impact for IF and IF+EF at 12 months.

The National Institutes of Health (NIH) defines Implementation Science (IS) as the process of applying evidence to the treatment or prevention of human disease.¹⁹⁻²⁰ A scientific study of methods to promote uptake of evidence into routine care to improve quality and effectiveness of healthcare through the study of influences on clinician and organizational behavior.²¹ This study is significant because it addresses testing of multimodal implementation strategies of an evidence-based intervention (CAPABLE) in a Medicaid setting to improve the quality and effectiveness of a waiver.

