1.14 DATA ANALYSIS

Preliminary analysis

The distributions of outcomes, mediators, and potential covariates will be assessed, outliers will be investigated by inspecting the residuals, and models described below will be fit with and without outliers to examine their influence on the results. Analyses will be implemented in SAS 9.4 as follows:

Aim A1 To test the effects of MiCAP with IF alone versus MiCAP with IF+EF with respect to the site-level outcomes of adoption and sustainability (**primary**) and beneficiary-level outcomes of ADL/IADLs, pain, depression, falls, emergency department (ED) visits and hospitalizations (**secondary**) over the next 12 months. Primary outcomes will be analyzed using a linear mixed effects model with repeated measures: 11 monthly measures of the SIC, 11 monthly summary records of clinician's actions based on EHR documentation, and monthly for 9 months measures from IF tools (statistical model #1). Covariates will include trial arm, variables used in randomization (site's size and CQAR score), and time entered as a class variable to model potentially non-linear patterns. In addition, we will use general liner model to analyze clinicians' fidelity training data. Log-rank test and Cox proportional hazard modeling will be employed to analyze time spent in each stage (treated as censored if a site does not complete a given implementation stage). The test of significance of the coefficient of the trial arm variable will yield the formal test of hypothesis associated with this aim for the main (time-averaged) effect of IF+EF v. IF alone. The analysis of secondary beneficiary-level outcomes will employ use generalized linear model with appropriately distributed errors and the random effect of site added to account for nesting of individuals within sites. For counts of falls and health service use, Poisson error distribution will be specified. Alternatively, as a zero-inflated Poisson or negative Binomial model based on the distribution of the counts will be fit. The explanatory variables including trial arm will be evaluated as predictors of zero inflation (whether or not the count is zero), and as predictors of the magnitude of the count when it is not zero. Pre-intervention MDS assessment will be used to obtain baseline version of each outcome, which will be included as a covariate to explain the variation in post-intervention outcomes.

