Aim A2 Mechanism-of-action To determine whether the effects of EF+IF versus IF on primary outcomes are mediated by clinician attitude or self-efficacy at 9 months. In addition to statistical model #1, statistical model #2 will be fit at the clinician level with site as a random effect to account for nesting of clinicians within sites. To test for mediation, trial arm will be treated as the independent variable; each of the potential mediators (one at a time) will be tested for their effect on the outcome variable. We will use a bias corrected bootstrapping analytic strategy⁸⁶⁻⁸⁷ based on 5000 bootstrap samples to estimate confidence intervals around the indirect effect of the trial arm on the outcome variable, through the mediator. To establish mediation, the 95% confidence interval around the indirect must not include 0.

Aim A3 To benchmark the effects of IF and EF+IF on beneficiary outcomes following implementation as compared to pre-intervention. The analysis of this aim will use 2 repeated measures of beneficiary outcomes: at the start of this study (pre-intervention) and in the following 12 months. Time by trial arm interaction will be included. The least square (LS) means according to the interaction term will be output from this model, and differences from pre-to-post CAPABLE will be evaluated for each arm to gauge the magnitude and practical meaning of improvements.

Exploratory Aim A4 To compare the primary and secondary outcomes within 12 months, potential mediators at 9 months, and baseline leadership and readiness for sites with SIC of $>50\%$ versus sites with $SIC \leq 50\%$ at 6 months in each arm. General or generalized linear models (as appropriate based on outcome or potential mediator distribution) will include the binary indicator of whether SIC at 6 months is $>50\%$ or $<50\%$ in interaction with the trial arm variable. Differences between LS means according to SIC level will be tested within each arm. Because these analyses are exploratory, in addition to formal tests of significance, the effect sizes will be estimated.

Exploratory Aim A5 To explore whether baseline site leadership and readiness moderate the impact of EF+IF compared to IF on primary and secondary outcomes within 12 months in order to determine which sites may

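### The unconditional claim of greater power for Aim 2 does not follow from its stated reason, and A2 neither specifies the baseline mediator nor limits interpretation where outcomes precede the mediator

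*Combined protocol and SAP*

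**What the plan says.** - **Power (section 1.15).** "The tests of mediation effects in Aim 2 will have an even greater power because of further reduction in error variance". No path size, clinician ICC, response rate or calculation is given for Aim 2. The sentence comes straight after the beneficiary-level result (detectable effect 0.14), but Aim A2 concerns the primary outcomes, which section 1.3 describes as "site-level outcomes of adoption and sustainability". Their detectable effect in section 1.15 is about 1.2 with 9 sites per arm.
- **Decision rule (section 1.14, Aim A2).** Mediation is established if "the 95% confidence interval around the indirect must not include 0". Mediators are handled singly: "each of the potential mediators (one at a time) will be tested for their effect on the outcome variable".
- **Model and bootstrap (section 1.14, Aim A2).** "statistical model #2 will be fit at the clinician level with site as a random effect"; no covariates are listed. The bias-corrected bootstrap is "based on 5000 bootstrap samples to estimate confidence intervals around the indirect effect", without naming the unit resampled.
- **Outcome (section 1.14, Aim A1).** The tested quantity is the "main (time-averaged) effect of IF+EF v. IF alone", with covariates arm, site size, CQAR score and time. For beneficiary outcomes, by contrast, Aim A1 does specify the "baseline version of each outcome, which will be included as a covariate".
- **Timing (sections 1.12 and 1.13).** EBPAS and GSE are taken at baseline (month 1 in the data collection table) and month 9. SIC is taken monthly from month 2 to month 12.

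**The concern.** Controlling for the mediator reduces residual variance in the outcome model. That helps the mediator-to-outcome path (b). It does nothing for the arm-to-mediator path (a), and the indirect effect needs both. A reader of section 1.15 would take a null A2 result as coming from the better-powered test, and so as evidence against the mechanism, when the plan gives no basis for that.

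Two further gaps affect how A2 will be read. The baseline value of each mediator is scheduled, but no A2 model is said to use it, which leaves the choice open until after the data are seen. And most of the time-averaged SIC outcome is recorded before the mediator. Section 1.11 has scorecard results reviewed weekly with clinicians, so the plan itself provides a route from earlier adoption to later attitude.

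**Working it through.** **1. The plan's benchmark.** Inputs from section 1.15: 9 sites per arm, 11 measures, correlation 0.7. Two-sided 0.05 and 80% power are assumed, since neither is stated.

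Variance factor = (1 + 10 × 0.7)/11 = 0.727; square root 0.853. Then 1.2/0.853 = 1.407 SD of the time-averaged site outcome. A two-sample t test with 16 df has 80% power there, so the 1.2 is reproduced. Power is 56% at d = 0.9 and 29% at d = 0.6.

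**2. Site-level reading.** Let b be the within-arm mediator-outcome correlation. Path a, in site SD, is mediated share × 1.407 / b. The joint test requires both paths significant at 0.05 (simulated, 40,000 replicates). The share and b are assumed; cells needing a above 2.05 SD are left out.

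| Mediated | b | Path a | Power, a | Power, b | Joint | Aim 1 |
|---|---|---|---|---|---|---|
| 25% | 0.3 | 1.17 | 65% | 22% | 14% | 80% |
| 25% | 0.5 | 0.70 | 29% | 56% | 15% | 80% |
| 25% | 0.7 | 0.50 | 17% | 92% | 15% | 80% |
| 50% | 0.5 | 1.41 | 80% | 56% | 43% | 80% |
| 50% | 0.7 | 1.01 | 51% | 92% | 46% | 80% |
| 100% | 0.7 | 2.01 | 98% | 92% | 90% | 80% |

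In the 25%, b = 0.7 row path b is almost certain to be found, yet power is 15% because path a is not. The planned bias-corrected bootstrap gives more: 28% (25%, b = 0.5) and 63% (50%, b = 0.7). Both are still below 80%, and its type I error at 18 sites was 7-11% in simulation.

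**3. Clinician-level reading.** 575/18 = 31.9, so about 32 clinicians per site. The SD of a site mean is sqrt((1 + 31 × ICC)/32): 0.20, 0.28 and 0.36 for assumed ICC 0.01, 0.05 and 0.10. Path a detectable with 80% power is 1.407 times that: 0.28, 0.40 and 0.50 clinician SD.

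Path a = share × total effect / b. This exceeds the total effect when share > b. With equal ICCs the two are tested on the same 18 sites with the same precision, and within-site data make path b nearly certain. For an assumed total effect of 0.2 clinician SD over the three ICCs (joint test, 1,500 replicates):

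| Mediated | b | Mediation power | Total-effect power |
|---|---|---|---|
| 25% | 0.2 | 29-71% | 20-55% |
| 25% | 0.3 | 14-38% | 20-50% |
| 50% | 0.2 | 79-99% | 20-51% |
| 50% | 0.3 | 46-90% | 19-50% |

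So the direction of the comparison with Aim 1 depends on quantities that section 1.15 does not give.

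**4. Timing of SIC.** Months 2-12 give 11 measures: 7 before month 9 (months 2-8), 1 at month 9, 3 after. Suppose there is no true mediation and month-9 attitude simply correlates with mean SIC over months 2-8. At an assumed correlation of 0.4-0.7 the planned bootstrap declares mediation in 15-59% of simulated trials at d = 1.2 and 7-26% at d = 0.6. At correlation 0.2 it does so in 3-4%.

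**5. Resampling unit.** With a = 0, b = 0.3 and ICC 0.01, 0.05, 0.10 (400 replicates), false indirect effects occur in 10%, 26% and 37% of trials if clinicians are resampled, and 9%, 11% and 8% if sites are.

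**The case against.** The strongest reply is that the plan's sentence may be right. Section 1.14 names the clinician level, and there a mediated share of 25-50% is often enough for mediation power to exceed total-effect power. At site level under full mediation it can do so too. This stands. A reader might infer that greater power is confined to strong mediation; that is true of one reading only. What fails is the absence of any condition and the reason offered.

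Second, nothing is decided by the sentence: the 18 available sites fix the sample size. That also stands, and it limits the matter to interpretation.

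Third, the plan is silent on covariates for model #2 and speaks of assessing potential covariates in the preliminary analysis. So the baseline mediator is unspecified; the documents do not show that it is excluded. The bootstrap unit is likewise unstated, although site nesting is modelled.

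Fourth, the month count is for SIC alone. Aim A1 also lists EHR action summaries, facilitator-tool measures, training fidelity and time in stage, and the documents do not say when sites reach the sustainability phase. The false-mediation rates depend wholly on an assumed correlation. They show that reverse direction could produce a positive result, not that one would be spurious. Confining the analysis to months 10-12 with adjustment for earlier SIC is no remedy: it detected constant-in-time mediation in only 3-7% of simulated trials.

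**Conclusion.** The concern holds in this form: the power statement is unconditional, its reason does not reach path a, and it is wrong over a wide plausible range. At site level with d = 1.2 and 25-50% mediated, joint-test power is about 14-46% against 80%. It is right over another range, chiefly at clinician level once the mediated share exceeds b. The documents do not support calling it always false. These figures rest on assumed path sizes, ICCs, mediated shares, full clinician response and 5% two-sided testing.

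A2's silence on the baseline mediator, and the absence of any caution where 7 of 11 SIC measures come before the mediator, are gaps in specification. Aim A2 is a named aim not labelled exploratory, so these should be corrected. None affects the sample size or the Aim 1 analysis. The resampling unit is a secondary clarification.

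**What to change.** **(a) Section 1.15.** Replace the Aim 2 sentence with: *Power for the indirect effect depends on both the arm-to-mediator and mediator-to-outcome paths, the first of which is limited by 18 randomised sites, and may be below or above that of Aim 1.* No cost.

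**(b) Section 1.14, Aim A2.** Add the baseline (month-1) value of each mediator as a covariate in the mediator and outcome models. Record its date relative to randomisation, training and external facilitator contact: section 1.2 lists randomisation before baseline assessments, and the month-1 row of the data collection table also holds training without giving the order. State a rule for clinicians with no month-1 value. The cost is 1 df per model. Detectable path a = 1.413 (15 df) × sqrt(1 − r²), so it falls from 1.41 to 1.35, 1.22 or 1.01 site SD for assumed baseline correlation r = 0.3, 0.5 or 0.7. If a fraction f of the arm effect is already present in the month-1 value, path a shrinks by r × f: 0.5 × 0.1 = 5%, or 0.5 × 0.25 = 12.5%.

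**(c) Section 1.14, Aim A2.** State that mediation of the all-months outcome is associational, because most SIC measures precede the mediator.

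**Clarification.** State that the bootstrap resamples sites within arm.

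All of this is wording; every measurement needed is already scheduled.
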